- Urinary ratio Beta 2 microglobulin/ creatinine $\geq 2\text{N}$

One subject that will meet one of these criteria above will be withdrawn from the study.

3.4.3.4. *QTc Withdrawal Criteria*

A subject that meets the criteria below will be withdrawn from the study. The QT correction formula used to determine discontinuation should be the same throughout the study.

- QTcB and QTcF > 500 msec, OR
- Change from baseline: QTc > 60 msec

Withdrawal decisions are to be based on an average QTc value of triplicate ECGs. If an ECG demonstrates a prolonged QT interval, obtain 2 more ECGs over a brief period, and then use the averaged QTc values of the 3 ECGs to determine whether the subject should be discontinued from the study.

The dose should not be escalated further if 2 or more subjects present a prolonged QT interval as defined above.

3.4.3.5. *Vital Sign Withdrawal Criteria*

The dose should not be escalated further if 2 or more subjects, within a dose-level, receiving IFB-088 experience a grade 3 vital signs (heart rate and/or blood pressure) adverse event that are deemed possible or probably related to study drug by the investigator.

The grading for adverse events is based on FDA's Guidance on Toxicity Grading Scale for Healthy Adult and Adolescent Volunteers Enrolled in Preventive Vaccine Clinical Trials:

Vital Signs*	Grade 3
Tachycardia (beats per minute)	> 130
Bradycardia - beats per minute**	< 45
Hypertension (systolic) - mm Hg	> 155
Hypertension (diastolic) – mm Hg	> 100
Hypotension (systolic) – mm Hg	< 80

*Assuming supine position, at least 5 min at rest conditions, not sleeping subjects, measurements on the same arm and several concordant results

**When resting heart rate is between 60-100 beats per minutes. Use clinical judgment when characterizing bradycardia among some healthy subject populations, for example, conditioned athletes.

Stopping rules for an individual subject, for the dose escalation and within a cohort are summarized in [Appendix 2](#).

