- 12-lead ECGs will be obtained at each time point during the study using an ECG machine that automatically calculates the heart rate and measures PR, QRS, QT, and QTc intervals. Subjects must rest in the supine position for at least 5 minutes before recording. The ECG may be recorded during the period of rest required before the measurements of supine BP and pulse. A qualified physician will review the ECGs promptly and any clinically important finding will be recorded on the appropriate CRF.
- At baseline in Day 1 pre-dose, ECG recordings will be conducted in **triplicate** (with an interval of approximately 10 - 30 minutes). The average value of each parameter will be considered as baseline value.
- ECG recordings will be performed post dose at specified time points (see Flow-Chart Time and Events).
- Parameters:
 - Measured parameters: HR, PR, QRS duration, QRS axis, QT;
 - Derived parameters: two corrections of the QT interval will be investigated: Fridericia's correction (QTcF) and Bazett's correction (QTcB);
 - Observations and comments on the quality of trace, on normality or abnormality.
- Refer to Section [3.4.3.3](#) for QTc withdrawal criteria and additional QTc readings that may be necessary.

Clinical Laboratory Assessments

The following parameters will be determined:

- **Hematology:**

Red blood cell (RBC) count, hemoglobin, hematocrit, white blood cell (WBC) count with differential (neutrophils, lymphocytes, monocytes, eosinophils, basophils), platelets, reticulocyte count.

- **Coagulation:**

Activated partial thromboplastin time (APTT), international normalized ratio (INR).

- **Biochemistry:**

Sodium, potassium, chloride, calcium, total bilirubin, alanine aminotransferase (ASAT), aspartate aminotransferase (ALAT), gamma-glutamyl transferase (GGT), alkaline phosphatases, total protein, albumin, urea, uric acid, bicarbonate, creatine phosphokinase (CPK), creatinine, glycaemia, lactate dehydrogenase (LDH), total cholesterol, HDL and LDL cholesterol, triglycerides.

- **Urinalysis:**

Specific gravity, pH, glucose, protein, blood, nitrites, leucocytes and ketones by dipstick, cytobacteriological exam (if abnormal results on dipstick); beta 2 microglobulin (B2M), proteinuria and creatinuria on urinary sample

- **Other screening tests:**

Hepatitis B antigen (HBs Ag), Hepatitis C antibodies (Anti-HCV Ab), Anti-HIV1 and Anti HIV2 antibodies (only at screening)

- **Alcohol breath test.**

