Tables by treatment group with the number of subjects having at least one medical or surgical history and the corresponding listing by subject will be edited; by system organ class and preferred term, if relevant (MedDRA). Tables by treatment group with the number of subjects having at least one previous treatment and concomitant treatment and the corresponding listing by subject will be prepared.

Baseline safety parameters:

Individual safety data (clinical laboratory, vital signs, ECG and physical examination) measured before the first drug administration will be checked for validity of entrance criteria, and abnormalities will be documented. Abnormal physical findings at baseline will be listed. Individual abnormalities before dosing will be flagged in data listings and presented along with post-dose measurements in the statistical appendices.

9.3.6. *Study drug and concomitant therapy*

Drug dispensing information and details of drug dosing (actual treatment received, actual dose received, date and time of drug intake) for each subject will be listed by treatment group.

Subjects who received concomitant treatments along with the study drug will be listed by treatment group and subject. If relevant, concomitant medications will also be summarized by anatomic class and therapeutic class (ATC drug dictionary) for each treatment group and overall subjects, presenting the frequency of subjects (n) taking a given medication and the number of occurrence of each medication.

9.3.7. *Safety Analyses*

Safety data will be presented in tabular and/or graphical format and summarized descriptively according to standard international guidelines.

9.3.7.1. *Criteria*

- Adverse events
- Vital signs: supine and standing systolic and diastolic blood pressure, pulse rate, tympanic temperature
- Standard 12-lead ECG
- Laboratory parameters: hematology, coagulation, biochemistry, urinalysis
- Physical examination
- Vigilance (Bond and Lader VAS)

9.3.7.2. *Methodology*

Laboratory data (hematology, biochemistry, coagulation and urinalysis), vital signs, vigilance VAS and ECG parameters, (raw data and changes from baseline) will be described.

In addition, vital signs, ECG and laboratory data could be compared to potentially clinically significant range (PCSA) to be specified in the SAP.

All these parameters will be listed by subject and assessment time. Data that is out of normal ranges will be flagged as well clinical significance.

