12. APPENDICES

12.1. Appendix 1: Liver Safety Algorithms

12.2. Appendix 2: Stopping rules

Stopping rules	Individual subject	Within a cohort/dose escalation
ALT or AST $\geq 3 \times$ ULN	1 subject	
ALT or AST $> 5 \times$ ULN		2 subjects
Triglycerides ≥ 5.6 mmol/L	1 subject	2 subjects
Creat $> 1,2 \times$ ULN or Increase in serum creat by $\geq 30 \mu\text{mol/L}$ within 24h or Increase in serum creat to $\geq 1,5 \times$ baseline within 7 days	1 subject	2 subjects
$\beta 2$ microglobuline $\geq 2 \times$ ULN	1 subject	2 subjects
Hematuria $> 2+$ on dipstick verified by cytologic exam, on 2 samples and considered at least possibly related to the IMP	1 subject	2 subjects
QTcB and QTcF > 500 msec or Change from baseline: QTc > 60 msec	1 subject	2 subjects
HR < 45 or HR > 130 bpm*	1 subject	2 subjects
SBP < 80 or SBP > 155 mmHg	1 subject	2 subjects
DBP > 100 mmHg	1 subject	2 subjects
Occurrence of a Serious Adverse Event considered at least possibly related to the IMP administration	1 subject	1 subject
Possibly drug related severe AEs in the same cohort, independent of within or not within the same system-organ		2 subjects
Clinically significant drug-related laboratory abnormalities of the same character		2 subjects
AUC _(0-inf) > 111.14 ng/ml.h ⁻¹ or Cmax > 23.77 ng/ml		1 subject (only for dose escalation)

* When resting heart rate is between 60-100 beats per minutes. Use clinical judgment when characterizing bradycardia among some healthy subject populations, for example, conditioned athletes.

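### Appendix 2 states the beta-2 microglobulin stopping rule without the urinary creatinine denominator that section 3.4.3.3 requires, and no text says which wording prevails

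*Combined protocol and SAP*

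**What the plan says.** Section 3.4.3.3 (Renal disorders) lists criteria that stop escalation when two or more subjects in a cohort meet them. One is the "Urinary ratio Beta 2 microglobulin/ creatinine" at 2N or more; N is not defined there. The section adds an individual rule: "One subject that will meet one of these criteria above will be withdrawn from the study".

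Section 3.4 closes by pointing to the table: "Stopping rules for an individual subject, for the dose escalation and within a cohort are summarized in" Appendix 2. The corresponding row there reads "microglobuline $\geq 2 \times$ ULN", with one subject in the individual column and two subjects in the cohort/escalation column. It mentions no creatinine and no sample type.

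Section 6.2 places the assay under urinalysis, as "beta 2 microglobulin (B2M), proteinuria and creatinuria on urinary sample". B2M is not in the blood biochemistry list. Section 1.3.2 presents urinary B2M as a sensitive marker of proximal tubular dysfunction and requires at least 2 L of water after dosing. Section 6.6.2 allows further water ad libitum.

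**The concern.** The two places attach identical actions to what reads as two different quantities. A ratio to urinary creatinine largely cancels urine dilution; a concentration does not. Someone working from the one-page table has nothing in the row to show that a denominator is missing, and section 6.2 lists B2M and urinary creatinine as separate results, so the ratio has to be derived.

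The kidney is the main target organ in the toxicology, and fluid intake is deliberately raised. The withdrawal of a subject, or a decision not to escalate, could therefore depend on which page was read. With eight subjects per cohort and a two-subject rule, one subject classified differently can change the escalation decision.

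**Working it through.** The plan gives no figure on this point to reproduce. The check sets the two texts side by side and then derives how the triggers relate.

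**Side by side**

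| | Section 3.4.3.3 | Appendix 2 |
|---|---|---|
| Quantity | urinary B2M/creatinine ratio | B2M |
| Threshold | ≥ 2N (N undefined) | ≥ 2 × ULN (which limit is not stated) |
| One subject | withdrawn | individual stop |
| Two subjects in a cohort | no further escalation | cohort/escalation stop |

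The actions match; the quantity does not. Because 6.2 measures B2M only in urine, a literal reading of the row is a urinary value.

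**Relation between the triggers.** Assume that N is the upper limit of normal of the ratio and that the ULN in Appendix 2 is a urinary concentration limit. Define:

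- r = (B2M / creatinine) / N, the ratio in multiples of its limit;
- C0 = ULN of B2M concentration / N, the urinary creatinine at which the two limits coincide;
- c = urinary creatinine / C0.

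Then B2M concentration / ULN = (r × N × creatinine) / (N × C0) = r × c.

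- Section 3.4.3.3 fires when r ≥ 2, whatever the value of c.
- Appendix 2 fires when r × c ≥ 2, that is, when r ≥ 2/c.

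| c | Appendix 2 fires at a ratio of | Section 3.4.3.3 fires at |
|---|---|---|
| 1/3 | 6N | 2N |
| 0.5 | 4N | 2N |
| 1 | 2N | 2N |
| 2 | 1N | 2N |
| 3 | 0.67N | 2N |

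In dilute urine (c < 1), a subject with r from 2 up to 2/c meets 3.4.3.3 and is missed by the table. In concentrated urine (c > 1), a subject with r from 2/c up to 2 meets the table and not 3.4.3.3. At c = 2 that includes a subject exactly at the normal limit.

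**Other case.** If the laboratory's reference limit for urinary B2M is itself expressed per creatinine, both rules reduce to r ≥ 2 and no decision differs. The documents do not give the reference range, so they do not settle which case applies.

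**The case against.** The strongest reply is that Appendix 2 is described as a summary, so the body text governs and the row is shorthand. Much of this stands. A reader might infer from the haematuria row, which keeps "on dipstick verified by cytologic exam, on 2 samples and considered at least possibly related to the IMP", that the B2M row is also meant as a complete, rival criterion. The table does not support that inference. The triglycerides row omits the condition that the subject is receiving IFB-088. The QTc row omits the averaging of triplicate ECGs. The vital-sign rows omit the relatedness condition and the measurement conditions. Abbreviation is common in the table. What remains is that this row changes the quantity being measured, and no precedence is stated.

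A reader might also try to size the effect from the water schedule: 1000 mL over T4–T12 is 125 mL/h and 500 mL over T12–T24 is 41.7 mL/h, a three-fold contrast. That would require urine flow to follow minimum intake and creatinine excretion to be constant, with water otherwise ad libitum. It also compares the 12 h and 24 h samples of the SAD part, for which this version already reports results. The on-treatment MAD urinalyses (D3, D6, D10, D13) are all taken in the morning before dosing, so the contrast does not describe them.

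A third inference would be that section 9.3.7.2 is deficient because it names no creatinine-normalised variable. It says: "Laboratory data (hematology, biochemistry, coagulation and urinalysis), vital signs, vigilance VAS and ECG parameters, (raw data and changes from baseline) will be described". But 9.3 leaves full analysis detail to the SAP, applying 3.4.3.3 already requires the B2M ratio, and no stopping rule uses a protein/creatinine ratio. This is not a defect.

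Finally, escalation is decided by a committee working under a charter (3.4.1), and the serum creatinine, haematuria and general laboratory rules also apply. These limit the consequences. They do not settle which B2M quantity is to be compared with its limit, and the committee's remit is escalation rather than individual withdrawal.

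**Conclusion.** The inconsistency is real and should be corrected. Sections 3.4.3.3 and 12.2 give the B2M rule in different terms with the same consequences, and no precedence is stated, although 3.4.3.3 is the natural governing text.

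Whether a decision would differ depends on two conditions: that someone applies the table literally, and that the ULN used is a concentration limit. If both hold, the table fires at 2/c × N instead of 2N, late in dilute urine and early in concentrated urine. That relation is exact once N is read as the upper limit of normal of the ratio. The values of c in this trial, and so the size of the discrepancy, cannot be derived from the documents. No sample size or planned analysis is affected.

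**What to change.** In Appendix 2, replace the B2M row with: *Urinary B2M/creatinine ratio ≥ 2 × ULN*, keeping the one-subject and two-subject columns. In 3.4.3.3, define N as the upper limit of normal of that ratio.

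The cost is wording only. B2M and creatinine are already measured on the urinary sample, so no new samples, visits or subjects are needed. No change to 9.3.7.2 is asked for.
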